4.3 Clinical Studies

4.3.1 Results from OBI-888-001

As of March 2020, a total of 17 patients with locally advanced or metastatic solid tumors have been enrolled, including 14 patients in the dose escalation phase (at doses of 5, 10, and 20 mg/kg) and 3 patients in the cohort expansion phase (at the selected recommended phase II dose [RP2D] of 20 mg/kg). The dose escalation phase is complete; no dose-limiting toxicities were reported and the maximum tolerated dose was not reached. The cohort expansion phase is ongoing, with OBI-888 administered at 20 mg/kg.

There have been 8 serious adverse events (SAEs) reported from 5 patients (from all 3 dose cohorts). All SAEs were assessed by the Investigator as unrelated to OBI-888. Two SAEs were Grade 5 (both in 1 patient), and the remaining SAEs were Grade 3 in severity. No patient has discontinued the study due to treatment related adverse events (AEs). Two (2/17, 11.7%) patients died on-study, both due to disease progression. OBI-888 in doses up to 20 mg/kg have been generally well-tolerated and no safety concerns have been noted.

In general, pharmacokinetic (PK) profiles following single-dose administration were similar across patients. Pharmacokinetic analysis showed no significant accumulation in peak concentrations (C_{max}) after multiple OBI-888 doses. However, accumulation of trough concentrations was observed in most patients (12/14, 86%). The mean trough concentrations at steady state increased with increasing OBI-888 dose (3.6 µg/mL for Cohort 1 [5 mg/kg], 5.1 µg/mL for Cohort 2 [10 mg/kg], and 11.3 µg/mL for Cohort 3 [20 mg/kg]). As expected for intravenous (IV) administration, C_{max} was achieved in most patients by the end of infusion. C_{max}/D values for each dose ranged from 0.246 to 0.275, suggesting that C_{max} was dose proportional across the doses tested. AUC_{last} exhibited higher variation across the doses tested, however, mean values of AUC_{last}/D and CL were similar across the dose groups. The mean Vz ranged from 4.4 to 5.7 L across the dose groups, which is consistent with the expected distribution volume of large protein therapeutics. The t_{1/2} was similar across the dose groups (30 hours).

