8.2.2 Regimen

OBI-888 will be administered as an IV infusion on Days 1, 8, 15, and 22 of each 28-day cycle in Part A and Part B of the study.

Treatment will continue until progressive disease, unacceptable toxicity, or decision by the Investigator or patient to discontinue treatment.

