8.3 Dose Modifications and Toxicity Management

Escalation to higher OBI-888 dose cohort is not permissible during the study.

Dose modifications for hematologic and non-hematologic toxicity and infusion reactions should be independently assessed at each visit. Recommendations for dose modifications for toxicity are provided in Table 8-1 below.

Toxicity Hold Dose % of Full Dose after **Recovery to Grade 0-1** Grade 1 Do not hold dose 100 75 Grade 2 Hold dose until resolution to Grade 0 or 1 Hold dose until resolution to Grade 0 or 1 Grade 3 75 NA Grade 4 Treatment should be discontinued

 Table 8-1
 OBI-888 Dose Modifications for Toxicity

Once the dose has been reduced for toxicity and found to be well tolerated, re-escalation may be permitted at the Investigator's discretion. If a subject requires dose reductions on more than 2 occasions for toxicity related to OBI-888, the subject should discontinue from the study.

All reasons for treatment modifications should be fully explained.

The study drug dose which is not administered within the permitted window period of ± 3 days, must be skipped, and the next dose will be administered as per protocol schedule. Any skipped dose due to safety reason and if medically justified, for OBI-888 treatment related or unrelated reasons, will not be captured as a protocol deviation for this study.

Treatment interruption for more than 2 consecutive doses for related or unrelated reasons may necessitate discontinuation of study treatment.

Treatment interruption for intercurrent non-treatment related adverse events will be at the Investigator's discretion and based on the well-being of the patient. All reasons for treatment interruption and delays should be fully explained. Treatment for hematologic and non-hematologic toxicity may be implemented as clinically indicated according to institutional guidelines. Refer Table 8-2 for therapeutic antiemetic and anti-diarrheal recommendations.

 Table 8-2
 Therapeutic Antiemetic and Anti-Diarrheal Recommendations

| Diarrhea and Abdominal Cramping | Nausea, Vomiting, or Anorexia |
|---|---|
| Dicyclomine: Recommended when the predominant issue is cramping or abdominal pain | 1st line: 5HT3-inhibitors |
| Diphenoxylate/Atropine or/and Loperamide | 2nd-line: Dexamethasone, ideally in combination with a 5HT3-inhibitor. Short term use can be very effective |
| | Other agents: anti-histamines; benzodiazepines; proton pump inhibitors; dopamine antagonists; cannabinoids |

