The infusion duration of Cycle 1 and Cycle 2 are 90 minutes, and can be reduced to 30-60 minutes from Cycle 3, if there were no infusion related adverse events on prior infusions and at the discretion of the Investigator.

a. C1D1 Pre-infusion serum samples can be drawn within 1 day prior-to the infusion.

b. Pre-infusion serum samples can be collected at any time prior to the infusion on the day of the infusion.

c. Post infusion samples at the end of infusion and later (at 1, 4, and 8 hours after the end of the infusion) can be collected in a window of ± 15 minutes.

d. For Cycle1 Days 2 and 4, a single sample will be collected (window ± 2 hours):

• 24 hours after end of infusion (for infusion at C1D1)

• 72 hours after end of infusion (for infusion at C1D1)

e. If there is change of the infusion rate or interruption of infusion, the PK sampling at Day 1 are to be collected from the exact time of completion of infusion to obtain the post-infusion samples at 1, 4, 8 hour at the end of infusion. Exact time of sample collection and the reason for interruption should be documented in the eCRF.

- ADA sample will be collected along with the pre-infusion PK samples according to the above table. No post-infusion ADA samples including C1D2 and C1D4 will be collected. For subjects with persistent antibodies at end of study, an additional ADA sample will be collected at 4 months after the end of study visit.
- g. Glycan analysis: pre-infusion and end of infusion in cycle 1 and 2 only. Residual PK and ADA samples will be pooled for glycan analysis after PK and ADA data are finalized.
- h. Samples to be collected on Day 1 of C4, C6, C8, C10, C12.
- i. Biomarkers:
 - ADCC (effector cell): pre-infusion blood sample will be collected at C1D1, C1D15, C2D22, C4D1 and end of study/early termination.
 - CDC/ADCC (humoral): pre infusion and end-of-infusion blood sample will be collected at C1D1, C1D8, and C1D15.
 - KIR, HLA, Fc receptor gamma genotyping: blood sample will be collected at C1D1 (pre-infusion) and end of study/early termination.

Table 9-3 Part B – Pharmacokinetic, ADA, and Biomarker Sampling Schedule

| Cycle (C) Screening C | | | | | | | | Cycle 2 | Every 2 cycles starting with Cycle 3 ^a | Every 2 cycles starting with Cycle 4 ^c | EoS / ET |
|---|-------------------|---------------------------|------------------|----------------|----|-----|-----|---------|---|---|----------|

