14.4 Pharmacokinetic Analysis

PK parameters will be calculated using a non-compartmental method from the PK samples collected on Dose 1 and will include C_{max} , total exposure (AUC), $t_{1/2}$, Cl, T_{max} , and V_d . To assess the attainment of steady state, trough (C_{min}) concentrations and peak concentrations (end of infusion) of each dose would be obtained directly from analytical data.

Summary statistics will be tabulated for the PK parameters of OBI-888 on Dose 1. Geometric means and coefficients of variation will be presented for C_{max} , AUC, $t_{1/2}$, Cl, and V_d . Median, minimum, and maximum will be presented for T_{max} .

To describe the dependency on dose, scatter plots of C_{max} and AUC versus dose will be provided. Summary statistics will be tabulated for the trough (C_{min}) concentration and peak concentrations (end of infusion) by dose and study day. To assess the attainment of steady state, geometric mean C_{min} values will be plotted versus study day by dose.

Pharmacometric methods may also be applied to further investigate OBI-888 exposure (e.g., accumulation of OBI-888, presence of dose- or time-dependent OBI-888 PK behavior, verification of influential factors on OBI-888 PK).

Based on the PK data (PK profile of first dose, steady-state trough serum concentrations, C_{trough} , or $C_{min,ss}$) and targeted concentration (IC₅₀ in xenograft model), a PK modeling will be carried out for various dose regimens including 15 mg/kg weekly, 15 mg/kg every 2 weeks, or 15 mg/kg q3 weeks. Simulated C_{trough} of desired regimen should be above the targeted serum concentration. The steady-state trough serum concentrations should be above 2.4 ug/mL, from the preclinical xenograft model exhibiting IC₅₀ (trough level at 50% tumor inhibition) of 2.4 ug/mL.

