2.3. PK Sampling Schedule

Blood (serum) samples will be collected at the following time points: C1D1 Pre-infusion (within 1 day prior-to the infusion), post infusion samples at the end of infusion and at 1 (\pm 15 min), 4 (\pm 15 min), 8 (\pm 15 min), 24 (\pm 2 h, on Day2), 72 (\pm 2 h, on Day4) and 168 hours (any time prior to C1D2 infusion) after the end of the infusion.

Statistical Analysis Plan: OBI-888-001 Review Status: Final Version: 2.0

Version Date: 02JUN2022

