- The percentage of extrapolated AUC should not exceed 20% of AUC∞ for each individual profile. If the percentage of extrapolated AUC is more than 20%, the individual AUC∞ result and the parameters depending on AUC∞ will be listed but flagged as not reliably calculated. They will generally not be included in descriptive statistics and statistical testing procedures.

AUMC_{last} (h²*µg/mL): Area under the first moment of the concentration time curve from time zero to time the last quantifiable time, calculated by log-linear trapezoidal rule.

AUMC_∞ (h²*μg/mL): Area under the first moment of the concentration-time curve from time zero to infinite time

CL (mL/h): Total body clearance following iv administration

-
$$CL = \frac{Total\ Dose\ Administrated\ in\ "\mu g"}{AUC_{\infty}}$$

V_z (mL): Volume of distribution following iv administration

Statistical Analysis Plan: OBI-888-001 Review Status: Final Version: 2.0

Version Date: 02JUN2022

-
$$V_z = \frac{CL}{\lambda}$$

V_{ss} (mL): Volume of distribution at steady-state following iv administration

-
$$V_{SS} = \frac{Total\ Dose\ Administrated\ in\ "\mu g" \times AUMC}{(AUC_{\infty})^2}$$

Dose proportionality

- To investigate the dose proportionality of AUC and Cmax, a statistical analysis using the power model will be conducted. The power model will have the form:
- $Y = a*(dose)^b$, where Y is the PK parameter, and a and b are the coefficient and exponent, respectively, of the power equation.
- By taking the natural logarithm (ln), the power model can be analyzed using linear regression and has the form:
- $ln(Y) = ln(a) + b*ln(dose) + error = \alpha + \beta*ln(dose) + error$,
- where α is the intercept, and β is the slope, and ln(dose) is based on the dose size for each subject.
- Estimates of slope and intercept along with their 90% confidence intervals will be reported. A minimum of 3 values per dose must be available for a given parameter to estimate dose proportionality using the power model.

All calculations will use the actual post-dose times recorded on the CRF. All computed PK parameters will be listed by subject and summarized by dose group in the Escalation Phase and by disease cohort in the Expansion Phase (mean, standard deviation, coefficient of variation, minimum, maximum, number of observations). Individual and mean (by time) concentrations versus time will be plotted for each dose on both linear and natural logarithm scales.

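### Cmin is summarised by study day with no condition on hours since the previous infusion, so permitted dosing shifts can outweigh the accumulation it is meant to show

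*Protocol*

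**What the plan says.** Dosing is weekly (protocol 8.2.2: "OBI-888 will be administered as an IV infusion on Days 1, 8, 15, and 22 of each 28-day cycle"), so the nominal trough interval is 168 h. For every pre-infusion sample after the first dose, footnote b of Tables 9-2 and 9-3 says only: "Pre-infusion serum samples can be collected at any time prior to the infusion on the day of the infusion". By contrast, the 24 h and 72 h samples carry a window of 2 h either way.

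Protocol 8.3 deals with doses not given "within the permitted window period of ± 3 days": such a dose "must be skipped, and the next dose will be administered as per protocol schedule". Table 9-1 allows 1 day either side for C1D8 and 3 days for later infusion visits.

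Protocol 14.4 tabulates Cmin by dose and study day, and plots geometric mean Cmin against study day to assess steady state. A later paragraph, on modelling of alternative regimens, adds: "The steady-state trough serum concentrations should be above 2.4 ug/mL".

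SAP Appendix III, 2.3 describes the last Dose 1 sample as "168 hours (any time prior to C1D2 infusion) after the end of the infusion". No infusion falls on Day 2; the sampling tables place this sample at C1D8. Appendix III, 3.4 uses actual post-dose times for the Dose 1 parameters and adds: "The percentage of extrapolated AUC should not exceed 20" percent. PK Table 2 and the mean-concentration figures use nominal time. Appendix III, 3.1 treats any value below the quantification limit that follows a measurable one as missing.

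**The concern.** A trough is interpretable as a trough only if the time since the last dose is roughly constant. Here that time can legitimately vary by days, and with a 30 h half-life a day matters. A patient dosed early looks as though drug is accumulating; a patient dosed late looks as though it is not. Short-interval samples stay in the mean at inflated values, while the lowest long-interval samples can drop out as unquantifiable. That asymmetry pushes the mean upward.

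At stake is the steady-state conclusion. Protocol 4.3.1 already reports trough accumulation in 12 of 14 patients without giving its size. The planned summary cannot show whether that reflects the drug or the intervals. No primary endpoint is affected.

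**Working it through.** **Inputs.** Half-life 30 h in all dose groups, and mean steady-state troughs of 3.6, 5.1 and 11.3 µg/mL at 5, 10 and 20 mg/kg (protocol 4.3.1). Interval 168 h (8.2.2). Windows of 24 h for C1D8 and 72 h for later visits (Table 9-1), and 72 h generally (8.3). Assay lower limit 468.75 ng/mL = 0.469 µg/mL (SAP Appendix III, 2.4). Assumption: mono-exponential decline. The documents give no figure for the shift effect, so there is none to reproduce.

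**Effect of interval on one trough.** Ratio to the 168 h value = 2^((168 − t)/half-life).

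| Hours since previous infusion | Half-life 30 h | Half-life 36 h |
|---|---|---|
| 96 (3 days early) | 5.28 | 4.00 |
| 144 (1 day early) | 1.74 | 1.59 |
| 192 (1 day late) | 0.574 | 0.630 |
| 240 (3 days late) | 0.190 | 0.250 |
| 336 (one dose skipped) | 0.021 | 0.039 |

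**Accumulation for comparison.** R = 1/(1 − 2^(−168/half-life)) = 1.021 at 30 h and 1.041 at 36 h. The 36 h value is a sensitivity case: back-calculating from the reported Cmax/dose and mean troughs, at an assumed 70 kg, gives about 32 to 36 h. At 30 h, a timing difference of 30 × log2(1.021) = 0.9 h already mimics the whole accumulation. A 72 h shift exceeds R until the half-life reaches about 113 h.

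**After a skipped dose.** At 30 h: 3.6 × 0.0206 = 0.07, 5.1 × 0.0206 = 0.11 and 11.3 × 0.0206 = 0.23 µg/mL, all below 0.469. At 36 h the highest is 11.3 × 0.0394 = 0.445, still below but close, so some patients at 20 mg/kg could remain measurable.

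**Effect on a cohort mean.** Assume cohorts of 5, 3 and 6: the first two are the anti-drug-antibody denominators in 4.3.1, the third is 14 − 5 − 3. Treat the reported means as geometric.
- One of 5 patients a day late: 3.6 × 0.574^(1/5) = 3.2, about 11% lower.
- One of 6 patients three days late: 11.3 × 0.190^(1/6) = 8.6, about 24% lower.

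Both exceed the calculated 2 to 4% accumulation.

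**Nominal-time outputs.** The last PK Table 2 column is 1.5 + 168 = 169.5 h. A C1D8 sample moved by 24 h enters that column with a 1.74-fold change.

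**Dose 1 profile if C1D8 is skipped.** With the 72 h sample last, the extrapolated share for a 1.5 h infusion is [(1 − e^(−kT))/(kT)] × e^(−72k), with k = ln2/30 = 0.0231 and T = 1.5. This gives 0.983 × 0.189 = 18.6%, against about 2% with the Day 8 sample. It passes 20% above a half-life of about 31 h. In Part A the 8 to 72 h span is 64/30 = 2.13 half-lives, and it falls short of the required 2.0 above 32 h.

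**The case against.** Much of the timing is already captured. Actual sample times are recorded (protocol 11.1), the Dose 1 parameters use them, and PK Listing 4 shows nominal and actual time with out-of-window samples marked. That protects lambda-z and AUC from timing shifts, and a claim that the Dose 1 parameters are biased by this would be wrong. It does not protect the Cmin summary by study day or the nominal-time table and figures.

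Several stronger readings are tempting and are not supported.
- **Troughs failing the 2.4 µg/mL target.** A reader might infer that late infusions would push the reported means below target. In 14.4 that figure is a target for simulated regimens, not a limit on each observed sample. The means would fall that far only if a whole cohort were late together.
- **A 5-fold shift at every trough.** Table 9-1 holds C1D8 to 1 day, which gives 1.74-fold. Nor is 5.3-fold a ceiling: two consecutive infusions moved 72 h in opposite directions change the interval by 144 h, or 27.9-fold. The documents do not report how often doses move.
- **A known 2% accumulation.** The 1.02 is calculated. No observed ratio is given, and 14.4 plans description, not a test for 2%.
- **A skipped C1D8 infusion deletes the 168 h point.** The documents are silent. The sample is scheduled by cycle day, and 11.1 permits altered or extra samples without requiring them.

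Two further objections stand as limits. Most Part B patients lack intensive sampling, so they have no Dose 1 parameters to lose and no lambda-z of their own. SAP Appendix III also specifies no Cmin-by-study-day output. However, PK parameters remain marked for the abbreviated report, and SAP section 11 does not list the trough analysis among those dropped, so protocol 14.4 still calls for it.

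**Conclusion.** The concern holds for the Cmin summaries and for the nominal-time 169.5 h column. At a 30 h half-life with mono-exponential decline, one permitted shift changes a patient's trough 1.74-fold (24 h) to 5.3-fold (72 h). A skipped dose leaves about 0.02 of the trough, probably unquantifiable and then dropped. Calculated accumulation is about 2% at 30 h and 4% at 36 h. The conclusion does not depend on the exact half-life, but how far the actual summaries are distorted depends on how often doses moved, which the documents do not give.

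For the Dose 1 profile, the defect is an unspecified sample. If it is not drawn, extrapolated AUC is about 19% at 30 h and exceeds the limit above about 31 h. CL and Vss, which are computed from AUC to infinity, would then be flagged and generally left out of the summaries for an intensively sampled patient.

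Table 9-1 and section 8.3 also disagree on the C1D8 window (1 day against 3 days), and these passages must be reconciled.

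**What to change.** 1. **Analysis rule (protocol 14.4 and SAP Appendix III).** For each pre-infusion sample, compute actual hours since the start of the previous infusion. Include it in the Cmin summary and plot only if that infusion was complete and the interval lies within a prespecified tolerance of 168 h. List the others with actual hours and quantification status. A tolerance of 12 h is one example. It still allows 2^(12/30) = 1.32-fold, so it is not enough alone. As support, report troughs adjusted to 168 h using the patient's lambda-z where estimable, and otherwise a pooled half-life or a model on actual time since dose. Apply the same interval rule to the 169.5 h column of PK Table 2, and name the Cmin output in Appendix III.
2. **Sampling rule (footnote b, Tables 9-2 and 9-3).** State that the C1D8 PK sample is drawn at the Day 8 visit whether or not the infusion is given.
3. **Reconcile** the C1D8 window in Table 9-1 with section 8.3, and the C1D2 label in SAP Appendix III, 2.3 with C1D8 in the sampling tables.

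The cost is a few sentences and a filter in the PK programs. Item 1 works on data already collected, because actual sample times are recorded and PK Listing 2 carries infusion start and end times. Item 2 helps only if sampling is still under way. The downside is fewer troughs in the summary, by a number the documents do not allow one to state.
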